5.4.2.3. Tapering of Ruxolitinib

If a subject has achieved CR or VGPR at Day 180, investigators may begin to taper the dose of ruxolitinib by 1 dose level provided corticosteroids have been discontinued for at least 8 weeks following institutional guidelines. Subjects who are still receiving calcineurin inhibitors or other agents for GVHD prophylaxis at this time may continue to do so at the treating investigator's discretion. In addition, subjects must not be experiencing any Grade 2 or higher hematologic toxicity related to ruxolitinib or symptoms of an active infection. Subsequent reductions to the dose of ruxolitinib may occur after an additional 56 days have elapsed provided the aforementioned requirements are still being met.

Investigators wishing to initiate a taper of ruxolitinib at an earlier timepoint may do so upon consultation with and approval from the sponsor's medical monitor.

If GVHD signs/symptoms worsen during the taper of ruxolitinib, the dose may be escalated by 1 dose level as indicated in Table 4; if the subject requires additional systemic therapy (includes restarting of corticosteroids), then the subject would be considered as having progression of disease and would be withdrawn from study treatment.

If subjects completely taper off ruxolitinib and GVHD signs/symptoms reappear at a later time, ruxolitinib therapy may be restarted at the treating investigator's discretion, and the subject would resume the assessment schedule using the original Day 1 as a reference point.

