7.3.2. Secondary and Efficacy Analysis

7.3.2.1. Duration of Response

Duration of response at Month 6 is the key secondary endpoint. For responders, the DOR is defined as the difference of the end of response and the start of response for subjects who have at least 1 response measurement. The start of a response will be the first visit where the subject achieves PR or better based on response criteria in Appendix B (MAGIC guidelines). The end of response will be the first visit after GVHD progression based on response criteria in Appendix B or death. Duration of response will be assessed using the Kaplan-Meier method for subjects who achieve a response. Median duration and 95% CI will be estimated. Subjects who are still responding at the time of database lock or discontinuation will be right-censored at the

time of last valid response assessment. Six-month DOR will be assessed when all subjects complete the Day 180 visit.

In addition, 3-month DOR will be assessed. Three-month DOR is defined as the time from first response until GVHD progression or death, when all subjects complete the Day 84 visit. Duration of response will be assessed using the Kaplan-Meier method for subjects who achieve a response.

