APPENDIX B. MAGIC GUIDELINES FOR STAGING AND GRADING ACUTE GVHD

Stage	Skin (Active Erythema Only)	Liver (bilirubin)	Upper GI	Lower GI (stool output/day)
0	No active (erythematous) GVHD rash	< 2 mg/dL	No or intermittent nausea, vomiting, or anorexia	Adult: < 500 mL/day or < 3 episodes/day. Child: < 10 mL/kg per day or < 4 episodes/day.
1	Maculopapular rash < 25% BSA	2-3 mg/dL	Persistent nausea, vomiting, or anorexia	Adult: 500-999 mL/day or 3-4 episodes/day. Child: 10-19.9 mL/kg per day or 4-6 episodes/day.
2	Maculopapular rash 25%-50% BSA	3.1-6 mg/dL	_	Adult: 1000-1500 mL/day or 5-7 episodes/day. Child: 20-30 mL/kg per day or 7-10 episodes/day.
3	Maculopapular rash > 50% BSA	6.1-15 mg/dL	_	Adult: > 1500 mL/day or > 7 episodes/day. Child: > 30 mL/kg per day or > 10 episodes/day.
4	Generalized erythroderma (> 50%) with bullae	> 15 mg/dL	_	Severe abdominal pain with or without ileus or grossly bloody stool (regardless of stool volume).

Acute GVHD Staging and Grading, MAGIC Guidelines

Overall clinical grade (based on most severe target organ involvement):

Grade 0: No stage 1-4 of any organ.

Grade I: Stage 1-2 skin without liver, upper GI, or lower GI involvement.

Grade II: Stage 3 rash and/or stage 1 liver and/or stage 1 upper GI and/or stage 1 lower GI.

Grade III: Stage 2-3 liver and/or stage 2-3 lower GI, with stage 0-3 skin and/or stage 0-1 upper GI.

Grade IV: Stage 4 skin, liver, or lower GI involvement, with stage 0-1 upper GI.

Response Definitions:

GVHD response assessments will be made with respect to changes in the organ stage relative to Study Day 1.

- Complete response (CR) is defined as a score of 0 for the GVHD grading in all evaluable organs. For a response to be scored as CR at Day 28 or later, the participant must still be in CR on that day and have had no intervening additional therapy for an earlier progression, mixed response (MR), or no response (NR).
- Very good partial response (VGPR) is defined as follows:
 - Skin: No rash, or residual erythematous rash involving < 25% of the body surface, without bullae (residual faint erythema and hyperpigmentation do not count).
 - Liver: Total serum bilirubin concentration < 2 mg/dL or < 25% of baseline at enrollment.
 - Gut:
 - Tolerating food or enteral feeding.
 - Predominantly formed stools.
 - No overt gastrointestinal bleeding or abdominal cramping.
 - No more than occasional nausea or vomiting.

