- Partial response (PR) is defined as improvement in 1 stage in 1 or more organs involved with GVHD symptoms without progression in others. For a response to be scored as PR at Day 28 or later, the participant must still be in PR on that day and have had no intervening additional therapy for an earlier progression, MR, or NR.
- Mixed response is defined as improvement in 1 or more organs with deterioration in another organ manifesting symptoms of GVHD or development of symptoms of GVHD in a new organ.
- Progression of disease is defined as deterioration in at least 1 organ without any improvement in others.
- No response is defined as absence of any improvement or progression as defined. Subjects receiving secondary therapy (including need to re-escalate steroid dose to greater than the Day 1 dose), will be classified as nonresponders.

Source: CIBMTR 2009, Martin et al 2009, Harris et al 2016.

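### A steroid restart for a flare during the ruxolitinib taper is progression under the protocol, but the SAP gives it no progression event in duration of response

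*Protocol*

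**What the plan says.** **Protocol 5.4.2.3.** A subject in CR or VGPR at Day 180 who has been off corticosteroids for at least 8 weeks may begin a ruxolitinib taper. An earlier taper needs the medical monitor's approval, and each further step waits another 56 days. If GVHD worsens in the taper, ruxolitinib may be raised by one level, but "if the subject requires additional systemic therapy (includes restarting of corticosteroids), then the subject would be considered as having progression of disease", and study treatment stops.

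**SAP 7.3.2.1.** On the event: "The end of response will be the first visit after GVHD progression based on response criteria in Appendix B or death". On censoring: "Subjects who are still responding at the time of database lock or discontinuation will be right-censored", at the last valid response assessment. The section plans a Kaplan-Meier analysis with the median and its 95% CI, 6-month DOR (the key secondary endpoint) and 3-month DOR.

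**SAP Appendix B.** The reference is Day 1: "GVHD response assessments will be made with respect to changes in the organ stage relative to Study Day 1". On progression: "Progression of disease is defined as deterioration in at least 1 organ without any improvement in others". On partial response: "Partial response (PR) is defined as improvement in 1 stage in 1 or more organs involved with GVHD symptoms without progression in others". A further sentence withholds PR at Day 28 or later from anyone who was given more therapy in the meantime for an earlier failure to respond. Under the no-response category: "Subjects receiving secondary therapy (including need to re-escalate steroid dose to greater than the Day 1 dose), will be classified as nonresponders".

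**The concern.** The two documents use different definitions of progression for the same subject. The protocol's taper rule is triggered by the need for therapy. The SAP's DOR event is triggered by organ stage compared with Day 1, and new therapy is not part of it. Only subjects in CR or VGPR are meant to taper at Day 180, so a flare can be real, and serious enough to need systemic treatment, while still milder than the disease at entry.

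Such a subject leaves response follow-up because GVHD came back. If that is not an event, the loss is informative and makes responses look longer than they were. SAP 10.1, which lists departures from the protocol's analyses, does not mention setting the taper rule aside, so this looks like an omission rather than a choice.

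**Working it through.** The plan states no DOR figure, so there is none to reproduce. The check is a trace of the rules, then timing, then size.

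**1. Trace one subject (illustrative).** Skin is stage 3 on Day 1. The subject reaches CR, tapers from Day 180, flares to skin stage 2 and restarts corticosteroids.

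| Moment | Protocol 5.4.2.3 | SAP 7.3.2.1 with Appendix B |
|---|---|---|
| Flare, before therapy | Worsening; ruxolitinib may be raised | Stage 2 against stage 3: PR, no event |
| Corticosteroids restarted | Progression; withdrawn from treatment | Possibly a nonresponder through the therapy sentences; not progression, no event |
| Afterwards | – | In effect censored, or an event only at death |

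A flare worse than Day 1 with no organ improved is already an event. A return to exactly the Day 1 stage is not Appendix B progression. Nor is a mixed picture, since "Mixed response is defined as improvement in 1 or more organs with deterioration in another organ manifesting symptoms of GVHD" is a separate category.

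**2. Do later data repair it?** Largely not. Staging at end of treatment (Protocol 7.6.1) would show stage 2, still better than Day 1. The 28-day staging in Protocol 6.4.2 is for subjects who stop for reasons other than GVHD progression. Under Protocol 6.4.3, a subject with confirmed progression or a new GVHD therapy moves to survival contact at least every 8 weeks.

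**3. Which DOR estimates can be reached?** DOR runs from first response. Assume first response on Day 7 to 28.
- 3-month mark: 7 + 84 = Day 91, to 28 + 91.3 = about Day 119. Both precede a Day 180 taper.
- 6-month mark: 7 + 180 = Day 187, to 28 + 182.6 = about Day 211. That is 7 to 31 days into a Day 180 taper.
- Earliest taper steps without early approval: Day 180, 180 + 56 = 236, and 180 + 112 = 292.
- A late first response moves the mark. For Day 56, 56 + 180 = Day 236, the second taper step.

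**4. Size.** Let R be the number of responders. With no earlier censoring and no later events, each restart not counted as an event leaves the curve 1/R too high:
- R = 37 (the Day 28 success threshold): 1/37 = 2.7 points
- R = 42 (60% of 70): 1/42 = 2.4 points
- R = 49 (70% of 70, an assumption): 1/49 = 2.0 points

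Illustration at 12 months, with assumed counts: R = 42, 25 still in response at month 6, and k restarts between months 6 and 12.

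| k | Restarts censored | Restarts counted | Gap |
|---|---|---|---|
| 1 | 25/42 = 0.595 | 24/42 = 0.571 | 0.024 |
| 2 | 25/42 = 0.595 | 23/42 = 0.548 | 0.048 |
| 3 | 25/42 = 0.595 | 22/42 = 0.524 | 0.071 |

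Two variations:
- Five other events after k = 2 restarts: censored 25/42 × 18/23 = 0.466, counted 18/42 = 0.429, a gap of 3.7 points. If the two subjects instead stay in the risk set and are alive at month 12, the estimate is 20/42 = 0.476 and the gap is the full 2/42 = 4.8 points.
- Five of the 42 censored evenly before month 6 (12 events, 25 at risk), k = 1: 0.691 against 0.691 × 24/25 = 0.664, a gap of 2.8 points.

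So 1/R is a working figure. Later events shrink it when the restart is censored, and earlier censoring widens it.

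**The case against.** The strongest reply is that Appendix B does not leave this subject a responder. Additional therapy disqualifies a later PR, and recipients of secondary therapy are nonresponders, with steroid re-escalation given as an inclusion rather than a complete list. The censoring sentence covers only subjects still responding, so a reader who infers that the SAP certainly censors this subject as a partial responder goes further than the text. That part stands. It does not supply an event, however: no response and progression are separate categories, and SAP 7.3.2.1 ends a response only at progression or death. Whether a restart at or below the Day 1 dose counts as secondary therapy is also unclear. The event is lost or put off until death, and DOR is overstated either way.

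Three further replies have weight.
- The tapering group is narrow, and raising ruxolitinib may settle a flare without steroids. There may be few restarts, or none.
- The 12-month estimate used above is not one that the SAP names. It shows the effect on a curve and median that the SAP does plan.
- Precision is poor anyway: at 25/42 a simple 95% half-width is 1.96 × √(0.595 × 0.405/42), about 15 points. One restart is small against that, though its error always favours longer response.

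An analyst might also apply the protocol's declared progression, since Protocol 9.4.2 speaks only of GVHD progression. The SAP wording, tied to Appendix B, does not direct that.

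**Conclusion.** The mismatch is real and should be closed. A taper flare that needs systemic therapy but stays better than Day 1 is progression under the protocol and has no progression event in the DOR analysis. If any such restart occurs, the later part of the Kaplan-Meier curve, and possibly the median, is overstated by about 2 to 3 points per restart for 37 to 49 responders, before other censoring or events. No particular shift in the median is claimed. DOR includes anyone who ever responds, so R may exceed the Day 28 count and the step would then be smaller.

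Two stronger readings are not supported. One is that DOR is biased upward outright: the number of restarts is unknown, and with none the bias is zero. The other is that the key secondary endpoint is seriously compromised: 3-month DOR is essentially unaffected, and 6-month DOR changes little on the standard taper schedule. It would be wrong in the other direction to say that only the first taper step can matter at 6 months, because approved early tapers or a late first response bring more of the taper inside that window. Day 28 ORR is not affected.

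**What to change.** Add to SAP 7.3.2.1 that progression declared under Protocol 5.4.2.3 (additional systemic therapy, including any corticosteroid restart, for GVHD worsening during the ruxolitinib taper) is a DOR event whatever the organ stage relative to Day 1. Date it at the start of that therapy, and state that this date replaces the SAP's visit-based dating for these events. This also settles mixed responses and returns to the Day 1 stage when they lead to a taper restart. The Appendix B-only definition can be kept as a sensitivity analysis.

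The cost is a short SAP addition. Steroid doses and concomitant medications are already collected (Protocol 7.4 and Table 5). The downside is that DOR may look slightly less favourable. Additional therapy outside the taper (Protocol 5.5.1) is a separate question on which this point makes no claim.

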5.4.3. Criteria and Procedures for Dose Interruptions or Adjustments of Corticosteroids

Corticosteroid doses should be tapered as per the recommended tapering schedule in Table 1 or as per institutional guidelines; further dose modifications may be made at the treating investigator's discretion.

5.4.4. Criteria for Permanent Discontinuation of Study Treatment

The occurrence of an unacceptable toxicity not caused by the underlying disease will be presumed to be related to study drug treatment and will require that the study drug be permanently discontinued. Unacceptable toxicity is defined as follows:

- Occurrence of an AE that is related to treatment with the study drug that, in the judgment of the investigator or the sponsor's medical monitor, compromises the subject's ability to continue study-specific procedures or is considered to not be in the subject's best interest.
- Persistent AE requiring a delay of therapy for more than 14 days, unless a greater delay has been approved by the sponsor.

5.5. Withdrawal of Subjects From Study Treatment

The decision to discontinue study treatment will not constitute study completion (see Section 5.5.3). In the event that the decision is made to discontinue study treatment, the treatment period will be considered complete, and the follow-up period will begin.

5.5.1. Withdrawal Criteria

Subjects **must** be withdrawn from study treatment for the following reasons:

- The subject has experienced an unacceptable toxicity.
- Relapse of the underlying malignancy.
- The subject is unable to tolerate ruxolitinib at a dose of 5 mg QD.
- Additional systemic therapy is required for GVHD progression or lack of response, including corticosteroids equal to or greater than the dose used on Study Day 1.
- Further participation would be injurious to the subject's health or well-being, in the investigator's medical judgment.
- The subject becomes pregnant.

- Consent is withdrawn.
- The study is terminated by the sponsor.
- The study is terminated by the local health authority, IRB, or IEC.

A subject **may** be withdrawn from study treatment as follows:

- If, during the course of the study, a subject is found not to have met eligibility criteria, then the medical monitor, in collaboration with the investigator, will determine whether the subject should be withdrawn from the study.
- If a subject is noncompliant with study procedures or study drug administration in the investigator's opinion, then the sponsor should be consulted for instruction on handling the subject.

5.5.2. Withdrawal Procedures

In the event that the decision is made to permanently discontinue the study drug, the subject will be withdrawn from the study, and the EOT visit should be conducted. Reasonable efforts should be made to have the subject return for a follow-up visit. These visits are described in Section 6. The last date of the last dose of study drug and the reason for subject withdrawal will be recorded in the eCRF.

If a subject is withdrawn from study treatment:

- The study monitor or sponsor must be notified.
- The reason(s) for withdrawal must be documented in the subject's medical record and in the eCRF.
- The EOT visit should be performed.
- The date of the EOT visit should be registered in the IVRS.
- Subjects must be followed for safety until the time of the follow-up visit or until study drug-related toxicities resolve, return to baseline, or are deemed irreversible, whichever is longest.

If the subject discontinues study treatment and actively withdraws consent for collection of follow-up data (safety follow-up or disease assessment), then no additional data collection should occur; however, subjects will have the option of withdrawing consent for study treatment but continuing in the follow-up period of the study for safety/efficacy assessments.

5.5.3. Study Completion

A subject will be considered as completing the study if they meet any of the following criteria:

- Subject dies and a date of death is available.
- Subject is known to have died; however, the date of death cannot be obtained. (NOTE: Every effort must be made to obtain the date of death.)
- Subject has discontinued study treatment and has withdrawn consent for collection of follow-up anticancer and survival data.

5.6. Concomitant Medications

5.6.1. Permitted Medications

Concomitant treatments and/or procedures that are required to manage a subject's medical condition (including prophylactic and/or supportive care medications as described in Section 5.2.2.4) during the study will also be recorded in the eCRF.

5.6.2. Restricted Medications

The following medications have restrictions on use during the treatment period of the study:

- Aspirin in doses exceeding 125 mg per day is not permitted. Low-dose aspirin (≤ 125 mg per day) is permitted unless clinically contraindicated.
- Coadministration with strong CYP 3A inhibitors; consider alternative agents with less CYP3A inhibition (Appendix C). Differences in individual sensitivity and variation CYP enzyme inhibition may result in the need for dose reduction of ruxolitinib and/or corticosteroids as appropriate. The sponsor medical monitor may be consulted for advice when using these agents.
- Coadministration with CYP3A4 inducers (Appendix C).
- If concomitant administration of an anticoagulant/antiplatelet medication is indicated, then caution and enhanced monitoring is required. History of thrombocytopenia should be a factor in the choice of anticoagulant and dose.

5.6.3. Prohibited Medications

The following medications are prohibited during the treatment period of the study:

- Any concurrent anticancer therapy (eg, chemotherapy, radiation therapy, surgery, immunotherapy, biologic therapy, hormonal therapy, or tumor embolization). Use of biologic agents for treatment of noncancer indications is permitted.
- Any secondary GVHD therapy due to insufficient response/progression on study treatment.
- Concomitant use of a JAK inhibitor.
- Initiating therapy with an investigational medication unless otherwise approved by the medical monitor.

6. STUDY ASSESSMENTS

All study assessments will be performed as indicated in the schedule of assessments (see Table 5), and all laboratory assessments will be performed as indicated in Table 6. Table 7 presents a summary of clinical laboratory analytes to be assessed. The order of assessments is suggested by the order of mention within the schedule. See Section 7 for instructions on each assessment. Further details of study procedures and assessments can be found in the study reference manual.

Table 5: **Schedule of Assessments**

		Screening								tment							_	
		Phase								ase ^a	1	h						Up Phase
Item	Section	-28 to -1	D1	D3	D 7	D14	D21	D28	D35	D42	D49	D56 ^b	D100	D180	D365 ^c	EOT	Safety ^d	Survival
Informed consent	7.1	Х																
Inclusion/exclusion criteria	3	х																
Contact IVRS	7.2	Х	Х					Х				Х	Х		Х	Х		Х
Demography/disease history	7.3	х																
Prior/concomitant medications	7.4	Х							:	x						x	х	
Supportive care medications	5.2.2.4	х		Х							x	х						
AE assessment	7.5.1	х								X						Х	Х	
Physical examination	7.5.2	х	Х		Х	Х	Х	Х	Х	Х	Х	Х	х		Х	Х	Х	
Vital signs	7.5.3	Х	Х		Х	Х	Х	Х	Х	Х	Х	Х	Х		Х	Х	Х	
ECOG performance status	7.5.4	Х	х		x	x	x	x	х	х	x	х	х		х	x	х	
12-lead ECG	7.5.5	Х							As in	licated						Х		
Acute GVHD grading and response assessment	7.6.1	Х	x		x	x	x	x	х	х	x	х	х	х	x	x	х	
Chimerism assessment	7.6.3	Х		As indicated														
PTLD assessment	7.6.4			As indicated														
Dispense study drug	5.1		Х					Х				Х			Х			
Study drug compliance	5.3		Х					Х				Х			Х	Х		
Steroid dose monitoring	5.3									X						Х		
Survival follow-up	6.4																	Xe

ECG = electrocardiogram; PTLD = post-transplant lymphoproliferative disorder. ^a A ± 2-day window is permitted to facilitate scheduling during the treatment phase.

^b After Day 56, visits will occur every 28 days and will include all Day 56 assessments.
 ^c The Day 365 visit will also serve as the regularly scheduled visit occurring every 28 days after Day 56 (ie, Day 364).

^d Thirty to 35 days after EOT. For subjects withdrawing due to reasons other than GVHD progression, GVHD status should be assessed every 28 days.

^e Every 8 weeks \pm 7 days.

Table 6: Laboratory Assessment
--

		Screening Phase		Treatment Phase ^a							ЕОТ	Safety					
Item	Section	-28 to -1	D1 ^b	D3	D 7	D14	D21	D28	D35	D42	D49	D56 ^c	D100	D180	D365 ^d		Follow-Up
Chemistry panel	7.5.6.1	Х	х	х	х	Х	Х	Х	Х	Х	Х	Х	Х		х	х	Х
Hematology	7.5.6.2	Х	х	Х	х	х	х	х	х	х	х	х	х		Х	х	Х
Hepatitis screening	7.5.6.4	Х		•													
Serum pregnancy test (childbearing females only)	7.5.6.3	х										х					
Urine pregnancy test ^e (childbearing females only)	7.5.6.3			х													
PK assessment ^f	7.7		х		Х	Х											
Correlative study blood collection	7.8	х	x		х	х		х				\mathbf{X}^{g}	х	х	х	х	

^a A ± 2-day window is permitted to facilitate scheduling during the treatment phase.
 ^b Day 1 laboratory assessments do not need to be repeated if screening assessments were performed in preceding 7 days.
 ^c After Day 56, visits will occur every 28 days and will include all Day 56 assessments.

^d The Day 365 visit will also serve as the regularly scheduled visit occurring every 28 days after Day 56 (ie, Day 364).

* Urine pregnancy tests are only required if medically indicated and should be confirmed with a serum pregnancy test.

^f Samples to be collected at predose and at 1 hour \pm 15 minutes, at 2 hours \pm 30 minutes, and between 4 and 8 hours postdose. ^g Day 56 only.

Serum Chemistries	Hematology ^a	Other
Albumin	Hematocrit	Serum pregnancy test
ALP	Hemoglobin	Urine pregnancy test ^b
ALT	Mean corpuscular volume	
AST	Platelet count	
Bicarbonate	Red blood cell count	
Blood urea nitrogen	Reticulocyte count	
Calcium	White blood cell count	
Chloride	White blood cell differential (5 parts):	Hepatitis Screening Tests
Creatinine	Basophils	
Glucose	• Eosinophils	Hepatitis B surface antigen
Lactate dehydrogenase	• Lymphocytes	Hepatitis B surface antigen antibody
Phosphorus	Monocytes	Hepatitis B core antibody
Potassium	Neutrophils	Hepatitis C virus antibody
Sodium	·······	HCV-RNA
Total bilirubin		HEV-KNA HBV-DNA
Total protein		

 Table 7:
 Clinical Laboratory Analytes

ALP = alkaline phosphatase.

^a Hematology and chemistry assessments will be performed locally.

^b Urine pregnancy tests are only required if medically indicated.

